7.8 Management of Nausea and Vomiting

Events of nausea and vomiting are known to be associated with olaparib and TMZ treatment. Patients should take ondansetron 8 mg PO once with the AM dose of TMZ for at least 1 cycle. Another anti-emetic can be substituted if clinically indicated.

These events are generally mild to moderate (CTCAE grade 1 or 2) severity, intermittent, and manageable on continued treatment. The first onset generally occurs in the first month of treatment for nausea and within the first 6 months of treatment for vomiting. For nausea, the incidence generally plateaus at around 9 months, and for vomiting at around 6 to 7 months.

Patients should receive additional appropriate anti-emetic treatment at the first onset of nausea or vomiting and as required thereafter, in accordance with local treatment practice guidelines.

As per international guidance on anti-emetic use in cancer patients (ESMO, NCCN), generally a single agent antiemetic should be considered, such as a dopamine receptor antagonist, antihistamine, or dexamethasone.

7.9 Interruptions for Intercurrent Non-Toxicity Related Events

Study treatment dose interruption for conditions other than toxicity resolution should be kept as short as possible. If a patient cannot restart study treatment within 4 weeks for resolution of intercurrent conditions not related to disease progression or toxicity, the case should be discussed with the CTEP Medical Monitor. Patients who are discontinued from the study for reasons other than progression of disease or treatment-related toxicity may be replaced.

All dose reductions and interruptions (including any missed doses), and the reasons for the reductions/interruptions are to be recorded in the eCRF.

Surgery indicated for the management of non cancer-related conditions (e.g. cholecystectomy, appendectomy) is permitted. Study treatment should be stopped at least 7 days prior to planned surgery. After surgery, study treatment can be restarted when the wound has healed. Surgery directed at sites involved by malignancy will usually require cessation of study participation for reasons of disease progression. Surgery that is related to side effects or toxicity from the drug should also result in cessation of study participation. Individual cases may be discussed with the CTEP Medical Monitor. No interruption of study treatment is required for any needle biopsy procedure however a blood count should be checked to ensure counts are adequate.

Because the AEs related to olaparib and TMZ may include asthenia, fatigue, and dizziness, patients should be advised to use caution while driving or using machinery if these symptoms occur.

8. PHARMACEUTICAL INFORMATION

A list of the adverse events and potential risks associated with the investigational or commercial agents administered in this study can be found in Section 10.1.

8.1 CTEP IND Agent

8.1.1 Olaparib (AZD2281) (NSC 747856)

Chemical Name: 4-[(3-{[4-(cyclopropylcarbonyl)piperazin-1-yl]carbonyl}-4fluorophenyl)methyl]phthalazin-1(2*H*)-one

Other Names: AZD2281; KU-0059436; CO-CE 42

Classification: PARP inhibitor

CAS Registry Number: 763113-22-0

Molecular Formula: C₂₄H₂₃FN₄O₃ M.W.: 434.46

Approximate Solubility: 0.1 mg/mL pH independent solubility across physiologic range

Mode of Action: Olaparib is an inhibitor of subclasses 1, 2, and 3 of polyadenosine 5' diphosphoribose polymerase (PARP-1, PARP-2, and PARP-3). In tumors that are deficient in the homologous recombination DNA repair pathway (example, BRCA mutants), inhibition of PARP by olaparib causes accumulation of DNA double-strand breaks and genomic instability. Olaparib may also enhance the effects of DNA damage caused by ionizing radiation and chemotherapy.

Description: crystalline solid

- How Supplied: AstraZeneca supplies and the Pharmaceutical Management Branch (PMB), CTEP, Division of Cancer Treatment and Diagnosis (DCTD) distributes olaparib as green, film-coated tablets in 100 mg and 150 mg strengths.
 - 100 mg tablets are 14.5 mm x 7.25 mm oval-shaped
 - 150 mg are 14.5 mm x 7.25 mm oval-shaped

Tablets are packaged in induction-sealed high-density polyethylene (HDPE) bottles with child-resistant closures. Each bottle contains 32 tablets with desiccant.

Tablet core components include active drug substance, copovidone, colloidal silicon dioxide, mannitol and sodium stearyl fumarate. Film coating contains hydroxypropyl methylcellulose (hypromellose), macrogol 400 (polyethylene glycol 400), titanium dioxide, iron oxide yellow and iron oxide black.

Storage: Store in a secure location below 30° C (86° F).

If a storage temperature excursion is identified, promptly return olaparib (AZD2281) to room temperature and quarantine the supplies. Provide a detailed report of the excursion (including documentation of temperature monitoring and duration of the excursion) to [contact] for determination of suitability.

Stability: Shelf-life studies are ongoing. Sites are not permitted to re-package tablets. Once the bottle is opened, olaparib tablets must be used within 3 months of the opening date; unused tablets should be discarded. Instruct patients not to open a bottle until they are ready to use it.

Route and Method of Administration: Oral. Take tablets without regard to meals.

Potential Drug Interactions: *In vivo* data indicate that CYP3A4/5 is important for olaparib metabolism and clearance in humans. For this reason, avoid concomitant administration of

strong and moderate CYP 3A4/5 inducers and inhibitors. Consult the protocol document or study investigator prior to making any dose adjustments related to potential drug-drug interactions.

In vitro data shows olaparib is a substrate for P-glycoprotein (P-gp), but not for organic anion-transporting polypeptides (OATP1B1 and OATP1B3), organic cation transporter 1 (OCT1), multi-drug resistance protein 2 (MRP-2) efflux transporter or breast cancer resistance protein (BCRP). Administration of strong P-gp inhibitors and inducers should be avoided with concurrent olaparib.

Based on *in vitro* data, olaparib inhibits CYP 3A4 and UGT1A1 enzyme systems and induces CYP 1A2, 2B6, and 3A4. Therefore, avoid concomitant administration of sensitive substrates, particularly those with narrow therapeutic ranges.

Olaparib is also an inhibitor of P-gp, OATP1B1, OCT1, OCT2, OAT3, multi-drug and toxin extrusion proteins (MATE1 and MATE2K) and a weak inhibitor of BRCP, but not an inhibitor of OATP1B3 or MRP-2. *In vitro* studies suggest that olaparib may increase exposure of substrates of these transport systems, although the clinical relevance is not clear. The manufacturer recommends that statins, in particular, should be administered with caution when given concomitantly with olaparib.

Patient Care Implications: Pre-clinical data indicate that olaparib adversely affects embryofetal survival and development. Therefore, women of child-bearing potential and their partners should agree to use two (2) highly effective forms of contraception starting at signing of the informed consent, throughout study participation and for at least one (1) month after the last dose of olaparib. It is not known whether olaparib is found in seminal fluid, so as a precaution, male study participants must use a condom during treatment and for three (3) months after the last dose and should avoid fathering a child or donating sperm during this same time period. The study investigator should discuss the most appropriate forms of highly effective contraceptive methods for each patient.

Lactation is a protocol exclusion criterion and not advised since there is potential for serious adverse reactions in breastfed infants. Advise lactating women to not breastfeed during study treatment and for one (1) month after receiving the last dose of olaparib.

Because the adverse events related to olaparib may include asthenia, fatigue and dizziness, patients should be advised to use caution while driving or using machinery.

There are no data on the effect of olaparib on wound healing, therefore as a precaution, olaparib treatment should be stopped at least 3 days prior to planned surgery. After surgery olaparib can be restarted when the wound has healed. No stoppage of olaparib is required for any needle biopsy procedure.

Study treatment should be discontinued for a minimum of 3 days before a patient undergoes therapeutic or palliative radiation treatment. Study treatment should be restarted within 4 weeks as long as any bone marrow toxicity has recovered.

Availability

Olaparib (AZD2281) is an investigational agent supplied to investigators by the DCTD, NCI.

Olaparib (AZD2281) is provided to NCI under a Collaborative Agreement between the Pharmaceutical Collaborator and DCTD, NCI (see Section 13.4).

8.1.2 Agent Ordering and Agent Accountability

NCI-supplied agents may be requested by eligible participating Investigators (or their authorized designee) at each participating institution. The CTEP-assigned protocol number must be used for ordering all CTEP-supplied investigational agents. The eligible participating investigators at each participating institution must be registered with CTEP, DCTD through an annual submission of FDA Form 1572 (Statement of Investigator), NCI Biosketch, Agent Shipment Form, and Financial Disclosure Form (FDF). If there are several participating investigators at one institution, CTEP-supplied investigational agents for the study should be ordered under the name of one lead participating investigator at that institution.

Submit agent requests through the PMB Online Agent Order Processing (OAOP) application. Access to OAOP requires the establishment of a CTEP Identity and Access Management (IAM) account and the maintenance of an "active" account status, a "current" password, and active person registration status. For questions about drug orders, transfers, returns, or accountability, call or email PMB any time. Refer to the PMB's website for specific policies and guidelines related to agent management.

Starter supplies will not be provided. Patients must be registered prior to agent ordering. Sites may request expedited orders Monday-Thursday when they provide courier information.

8.1.2.1 Agent Inventory Records

The investigator, or a responsible party designated by the investigator, must maintain a careful record of the receipt, dispensing and final disposition of all agents received from the PMB using the appropriate NCI Investigational Agent (Drug) Accountability Record (DARF) available on the CTEP forms page. Store and maintain separate NCI Investigational Agent Accountability Records for each agent, strength, formulation and ordering investigator on this protocol.

8.1.3 Investigator Brochure Availability

The current versions of the IBs for the agents will be accessible to site investigators and research staff through the PMB OAOP application. Access to OAOP requires the establishment of a CTEP IAM account and the maintenance of an "active" account status, a "current" password and active person registration status. Questions about IB access may be directed to the PMB IB Coordinator via email.

8.2 Commercial Agent

8.2.1 Temozolomide (NSC 362856)

Chemical Name: 3,4-dihydro-3-11 methyl-4-oxoimidazo[5,1-d]-as-tetrazine-8-carboxamide

Other Names: Temodar[®], Temodal[®], Temcad[®]

Classification: Alkylating Agent

CAS Registry Number: 85622-93-1

Molecular Formula: C₆H₆N₆O₂

M.W.: 194.15

Mode of Action: Temozolomide is not directly active but undergoes rapid nonenzymatic conversion at physiologic pH to the reactive compound 5-(3-methyltriazen-1-yl)-imidazole-4-carboxamide (MTIC). The cytotoxicity of MTIC is thought to be primarily due to alkylation of DNA. Alkylation (methylation) occurs mainly at the O6 and N7 positions of guanine.

How Supplied: Temozolomide is commercially available. Please refer to the FDA-approved package insert for this drug.

Capsules are supplied in child-resistant sachets containing the following capsule strengths: 5 mg, 20 mg, 100 mg, 140 mg and 180 mg.. The dose of temozolomide is based on body surface area (BSA) and then rounded off to the nearest 5 mg.

Storage: Store at 25°C (77°F); excursions permitted to 15°–30°C (59°–86°F).

Stability: The molecule is stable at acidic pH (<5) and labile at pH >7.

Route of Administration: Oral

Method of Administration: Take each day's dose of capsules at one time, with a full glass of water. Temozolomide will be administered orally. The capsules should be swallowed whole and never chewed. The incidence of nausea and vomiting is decreased when temozolomide is taken on an empty stomach.

9. STATISTICAL CONSIDERATIONS

9.1 Study Design/Endpoints

9.1.1 Study Design

A single arm, open label design will be used to determine the efficacy of the combination of olaparib and TMZ in patients of advanced uterine LMS.

9.1.2 Primary Endpoint

The primary endpoint of this study is the confirmed ORR (complete response + partial response) as measured by RECIST version 1.1 criteria. Responses must occur within the first 6 months of study treatment for the purpose of evaluating the primary endpoint. The ORR will be reported with a 95% confidence interval.

FDA approved second-line and later line agents used in uterine LMS based on phase 3 clinical trial data include trabectedin (a DNA damaging cytotoxic agent) and pazopanib (an antiangiogenic receptor tyrosine kinase inhibitor). A recent phase 3 clinical trial randomized patients with LMS and another sarcoma subtype (liposarcoma) to trabected in or dacarbazine. Dacarbazine, an intravenous chemotherapeutic with an analogous mechanism of action to oral TMZ, has often been used as a control arm in phase 3 sarcoma studies, and was used by the European Organization for Research and Treatment of Cancer to establish benchmarks for assessing the activity of novel second line agents in STS (Van Glabbeke et al., 2002). In the randomized phase 3 study of trabected in versus dacarbazine, patients were required to have previously received an anthracycline-based regimen and there was no upper limit on the number of prior treatments received. In a recently reported subset analysis of the uterine LMS cohort from this study, the ORR was 11% for trabectedin and 9% for dacarbazine and this difference was not statistically significant (p=0.82) (Demetri et al., 2016; Hensley et al., 2017). Similarly, in an analysis of 318 LMS patients enrolled on a single-arm, open-label trabectedin extended access program available after progression on standard chemotherapy, the response rate was 7.5% (Samuels et al., 2013).

In another phase 3 study patients with several sarcoma subtypes who had received at least one regimen containing anthracycline and a maximum of four previous lines of systemic therapy were randomized to pazopanib versus placebo (van der Graaf *et al.*, 2012). In a recently published subset analysis of this study (and the preceding phase 2 study) limited to uterine sarcomas (90% had LMS), the response rate to pazopanib was 10% (Benson *et al.*, 2016).

In view of the above, we will consider a response rate of 10% to be inactive and unworthy of further study, whereas a response rate of 35% would be promising for further study among patients with advanced LMS treated with at least one prior systemic regimen. A response rate of 35% for the TMZ + PARPi combination would also be suggestive of superior efficacy over TMZ monotherapy in sarcoma. As discussed above, dacarbazine, the IV analogue of TMZ, was associated with a response rate of 9% among LMS patients treated on the randomized phase 3 study of trabectedin versus dacarbazine (Demetri *et al.*, 2009). Furthermore, in a phase 3 randomized study of eribulin versus dacarbazine which included 75% LMS patients, the response rate to dacarbazine was 5% (Schoffski *et al.*, 2016). In a randomized study of gemeitabine and dacarbazine versus dacarbazine alone, the response rate to dacarbazine was 4% (Garcia-del-Muro *et al.*, 2011).

9.1.3 Analysis Plan

A one-stage binomial design will be used evaluating an objective response rate of at most 10% (null hypothesis) versus at least 35% (alternative hypothesis). The design calls for 22 patients. If 5 or more from the total sample of 22 respond, the treatment is considered worthy of further consideration. This design yields 93% power and 1-sided type I error of 6% to test for a response rate of 10% vs. 35%. The study team believes this design, and an observed response rate of 22.7%, would reflect a clinically meaningful finding worthy of further evaluation considering currently available treatment options and results of other studies as described above. A minimum of 22 to a maximum of 25 (22 + 3) patients will be required for the study, allowing for patients deemed ineligible or withdrawing consent prior to the first dose of study treatment (that is, 2-3 additional patients will be recruited to account for non-evaluable patients).

The proposed endpoints are reflective of recently reported phase 2 studies conducted specifically in LMS. Phase 2 studies of pembrolizumab (George *et al.*, 2017), alisertib (Hyman *et al.*, 2017), ixabepilone (Duska *et al.*, 2014) and ziv-aflibercept (Mackay *et al.*, 2012) conducted specifically in LMS used Simon 2 stage designs with objective response rate as the primary endpoint and a null hypothesis of 5% as compared an alternative hypothesis of between 20-25%, and none met this endpoint (Ben-Ami *et al.*, 2017; Hyman *et al.*, 2017; Duska *et al.*, 2014; Mackay *et al.*, 2012). After review of all recently published LMS-specific studies, the highest benchmarks for activity were used in phase 2 studies of trabectedin and sunitinib (10% considered inactive and 30% active) (Monk *et al.*, 2012; Hensley *et al.*, 2009).

9.2 Sample Size/Accrual Rate

Using the ECTCN network and recognizing that LMS is a relatively common sarcoma subtype, we expect to enroll approximately 2 patients per month across all participating centers. Thus, we anticipate full accrual after approximately 10 months.

	Ethnic Categories					
Racial Categories	Not Hispanic or Latino		Hispanic or Latino		Total	
	Female	Male	Female	Male		
American Indian/ Alaska Native	0	0	0	0	0	
Asian	1	0	0	0	1	
Native Hawaiian or Other Pacific Islander	0	0	0	0	0	
Black or African American	4	0	0	0	4	
White	12	0	3	0	15	
More Than One Race	2	0	0	0	2	
Total	19	0	3	0	22	

PLANNED ENROLLMENT REPORT

PHS 398 / PHS 2590 (Rev. 08/12 Approved Through 8/31/2015)

OMB No. 0925-0001/0002

9.3 Stratification Factors

Not applicable.

9.4 Analysis of Secondary Endpoints

9.4.1 Secondary Endpoints

9.4.1.1 Toxicity

Adverse events will be recorded at each clinical visit and will be categorized according to NCI CTCAE version 5.0. Adverse event rates will be reported as counts and percentages per adverse event by grade.

9.4.1.2 Progression-Free Survival

PFS is defined as the time from first treatment with the study drug to the earliest of either disease progression or death from any cause. Patients who are alive and progression free will be censored at the time of their last tumor assessment. The Kaplan-Meier method will be used to evaluate time to event endpoints. Median PFS will be reported with a 95% confidence interval.

9.4.1.3 Integrated Correlatives

The association between ORR, PFS, and the results of integrated assays evaluating for presence of HR deficiency in the tumor will be evaluated. The two integrated assays are genomics for alterations in HR genes and RAD51 foci formation. Both of these assays report binary results. The rate of response will be compared between binary variables using the Fisher's exact test. The log-rank test will be used to compare PFS between binary variables. Additional results from whole exome sequencing and RNAseq analysis on study samples will be reported in a descriptive fashion.

9.4.1.4 Exploratory Correlatives

The association between ORR, PFS, and the exploratory assays will be evaluated in a preliminary fashion. The exploratory assays include SLFN11 and MGMT expression by IHC. SLFN11 and MGMT mRNA expression may also be performed. SLFN11 and MGMT expression are reported as a continuous variable. Logistic regression will be used to estimate the odds of response for every unit increase in protein expression. Cox-regression will be used to evaluate the association between PFS and protein expression. Graphical displays such as box plots and Kaplan-Meier plots will be used to visualize the data.

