5.7.1.3 Submission of Sequencing Results Previously Obtained as Standard of Care

WES results are available for 16 of the 22 patients who participated on 10250 using tumor biopsies obtained for the study. No results are available for the remaining patients because tissue was not available for various reasons, including technical issues accessing the tumor during the biopsy or poor tumor content. To better understand whether patients with genomic alterations in the HR pathway are more likely to derive clinical benefit from the study treatment and to perform the most complete analysis feasible, we would like to request that sites submit next generation sequencing (NGS) results from NGS assays previously performed as standard of care (i.e. Foundation Medicine, Caris, institutional platform). These reports would be redacted per institutional practice and submitted to the study PI.

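### With few responders expected, specify Firth-penalised logistic regression for the SLFN11 and MGMT response analyses: default maximum likelihood exaggerates any real association

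*Combined protocol and SAP*

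**What the plan says.** Section 9.4.1.4 treats SLFN11 and MGMT expression as continuous and describes the evaluation as preliminary. For response, "Logistic regression will be used to estimate the odds of response for every unit increase in protein expression". It does not give the estimator, the interval method, the unit of expression, or what happens if the fit fails. Box plots are also planned.

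Three other places bear on how much data this model will have:

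- Section 9.1.3: "The design calls for 22 patients", and "If 5 or more from the total sample of 22 respond, the treatment is considered worthy of further consideration".
- Section 5.6: SLFN11 and MGMT rank third and fourth for tissue and are optional.
- Section 5.7.1.3, on the top-ranked assay: "WES results are available for 16 of the 22 patients who participated on 10250 using tumor biopsies obtained for the study".

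The number of patients with SLFN11 or MGMT results is not stated. For the binary HR assays, Section 9.4.1.3 uses Fisher's exact test for response, which is a small-sample method. The continuous markers get none.

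**The concern.** Logistic regression without further description is normally fitted by maximum likelihood. Its slope is biased away from zero when there are few events. If a marker value separates responders from non-responders completely, the estimate is infinite.

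Objectives 1.3.1 and 1.3.2 ask whether these markers are associated with benefit. If they are, the reported OR would tend to be too extreme: too high for SLFN11, and too close to 0 for MGMT, where high expression is expected to mean resistance. What is at stake is the size of an exploratory estimate and the coverage of its interval.

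**Working it through.** **1. The plan's own figure.** For the rule of at least 5 responders in 22, the exact binomial gives P(X ≥ 5 | 10%) = 0.0621 and P(X ≥ 5 | 35%) = 0.9284. This agrees with the stated 6% type I error and 93% power.

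**2. Responders available (assumed).**
- All 22 patients: 0.10 × 22 = 2.2 to 0.35 × 22 = 7.7. The success boundary is 5/22 = 22.7%.
- Low case of 16, borrowed from the whole exome sequencing yield: 0.10 × 16 = 1.6 to 0.35 × 16 = 5.6. At 22.7% it is 0.227 × 16 = 3.6, taken as 4.

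**3. Model.** Fix the number of responders. Draw the marker from N(0,1) in non-responders and from N(δ,1) in responders. The log density ratio is δx − δ²/2, so the true logistic slope is exactly δ = log(OR) per within-group SD. ML maximises l(β). Firth maximises l(β) + ½ log|I(β)|, where I is the information matrix. The ORs are assumed, because the plan gives none.

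**4. Results** (1,500 to 2,500 data sets per row). ML means leave out separated data sets. ML medians count them as infinite.

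| Patients, responders | True OR (log) | ML mean log-OR | ML median OR | Firth mean log-OR | Firth median OR | Complete separation |
|---|---|---|---|---|---|---|
| 22, 5 | 1 (0) | −0.01 | 1.00 | −0.01 | 1.00 | <0.1% |
| 22, 5 | 2 (0.69) | 0.93 | 2.14 | 0.71 | 1.87 | 0.2% |
| 22, 5 | 3 (1.10) | 1.54 | 3.54 | 1.14 | 2.74 | 0.9% |
| 16, 4 | 1 (0) | 0.02 | 1.00 | 0.02 | 1.01 | 0.1% |
| 16, 4 | 2 (0.69) | 1.08 | 2.30 | 0.73 | 1.89 | 0.8% |
| 16, 4 | 3 (1.10) | 1.67 | 3.66 | 1.12 | 2.63 | 3.0% |
| 16, 4 | 5 (1.61) | 2.52 | 7.16 | 1.60 | 3.83 | 13.1% |

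Repeat runs agree to within simulation error. For 16 patients at OR 3, for example, the ML median ranges from 3.66 to 3.81 and separation from about 3% to 4%.

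**5. Reading the table.**
- Mean log-OR at OR 3: 1.54/1.10 = 1.40 and 1.67/1.10 = 1.52, so 40% to 52% too large.
- Median OR, the typical result. At OR 2: 2.14/2 = 1.07 to 2.30/2 = 1.15. At OR 3: 3.54/3 = 1.18 to 3.81/3 = 1.27.
- With 22 patients and 4 or 5 responders, ML exceeds twice the true OR in 21–23% of data sets at OR 2 and 27–29% at OR 3. Firth does so in 11–13% and 14–15%.
- Root mean squared error of the log-OR, 16 patients and 4 responders: ML 1.04, 1.54 and 2.02 at OR 1, 2 and 3; Firth 0.68, 0.77 and 0.89. The ML figures again leave out separated data sets.
- Interval coverage in the same case at OR 3: 89.5% for the ML likelihood-ratio interval, 96.3% for the penalised one.

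**6. Separation at the edges.** With no association, every ordering is equally likely, so the exact chance is 2/C(22,5) = 2/26,334 (under 0.01%) or 2/C(16,4) = 2/1,820 (0.1%). It becomes frequent only with a very strong effect and very few responders: at OR 5 with 2 responders, 19% (22 patients) or 27% (16 patients).

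**7. What Firth costs.**
- The median OR falls below the truth (table).
- Mean fitted response probability rises towards 0.5: from 0.227 to 0.248 with 5 responders in 22.
- At nominal 5% with 22 patients and OR 2, the penalised likelihood-ratio test rejects in 20–23% of data sets and the ML likelihood-ratio test in 27–30%. However, the two tests reject 3.0–4.0% and 5.0–6.4% of the time with no association. Once size is equalised, power is the same (24% and 24% with 4 responders; 30% and 30% with 5).

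**The case against.** The strongest defence is that the plan contains no error. It never says maximum likelihood, and Firth's method is itself logistic regression. The analysis is labelled preliminary, and the box plots would make separation obvious. This stands in part: ML is my reading of the usual default. But nothing in the plan points to anything else, and a better-suited method is readily available.

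Several stronger readings are tempting and are not supported:

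- A reader might infer that ML always overstates the OR. With no association it has no bias. Where there is one, the large figures are means driven by nearly separated samples; the typical excess is about 7–15% at OR 2 and 14–27% at OR 3.
- A reader might infer that separation is likely to break the analysis. With 22 patients and 5 responders it is about 1% at OR 3.
- A reader might infer that 16 patients is the number for these markers. That yield is for sequencing, which needs extracted DNA and RNA. SLFN11 and MGMT use unstained slides, and their yield could be higher or lower.
- A reader might infer that the OR will decide whether a marker is pursued. No section attaches a decision rule, alpha level or target effect to it.
- A reader might infer that Firth is free, or that the Cox model for PFS needs the same change. Step 7 shows the costs, and the documents give no PFS event count from which to argue the second.

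**Conclusion.** The point holds as an inexpensive improvement to an exploratory analysis. If SLFN11 or MGMT is truly associated with response, default ML exaggerates the association: by about 0.4 to 0.6 on the mean log-OR at OR 3, and by roughly a tenth to a quarter on the median OR across OR 2 to 3. Firth removes nearly all the mean bias, is always finite and has smaller overall error. On the median it errs modestly the other way.

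This rests on four assumptions: ML is what the plan intends; there are about 4 or 5 responders (expected range about 2 to 8); 16 to 22 patients have marker results; and the marker is roughly normal with OR 1 to 5 per SD. Neither method cures the imprecision, since power at OR 2 is only about 20–30%. The primary response-rate conclusion and the Fisher's exact tests in Section 9.4.1.3 are untouched.

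**What to change.** In Section 9.4.1.4, name Firth-penalised logistic regression with profile penalised-likelihood 95% confidence intervals as the estimator for the SLFN11 and MGMT response analyses. State the unit in which the OR is expressed, for example per SD or a fixed step on the assay scale. Report the number of patients and responders behind each estimate.

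Section 5.7.1.3 shows that 22 patients had already participated and that sequencing results existed, so label this as a late change to an exploratory analysis. Say whether it was made before the SLFN11 and MGMT results were seen; the documents do not settle that.

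The cost is a few words and a software option, with no extra patients or tissue. The write-up should note that the median OR is pulled modestly towards 1 (about 1.9 for a true 2, and 2.7 for a true 3), and that fitted probabilities shift towards 0.5 and should not be reported without an intercept correction.
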